6.1 Adverse event definitions

The term "adverse event" could include any of the following events which develop or increase in severity during the course of the study, after administration of the study product:

Page 70 of 176

a) Any unfavorable and unintended signs, symptoms or disease temporally associated with the use of a medicinal product, whether or not considered related to the condition under study and the study product;

b) Any abnormality detected during physical examination.

The medical conditions present at the initial trial visit that do not worsen in severity or frequency during the trial will not be defined as AEs but as be considered baseline medical conditions. For the purpose of this trial, disease progression and relapse will be considered as treatment failure, not as an AE.

The observation time for AEs starts when the treatment is initiated until day 21 (3 weeks after last drug administration).

These data will be recorded on the appropriate CRF sections, regardless of whether they are thought to be associated with the study or the drug under investigation. Associated with the use of the drug means that there is a reasonable possibility that the event may have been caused by the drug (see also relatedness definitions below).

6.1.1 Severity grading

Adverse signs or symptoms will be graded by the Investigator as mild, moderate, severe or life threatening according to the following definitions:

Grad	e Definition
1	Mild : the subject is aware of the event or symptom, but the event or symptom is easily tolerated.
2	Moderate : the subject experiences sufficient discomfort to interfere with or reduce his or her usual level of activity.
3	Severe: significant impairment of functioning: the subject is unable to carry out his or her usual activities.
4	Life threatening or disabling
5	Death related to adverse events

6.1.2 Relatedness

Relatedness will be assessed as defined below based on the temporal relationship between the AE and the treatment, known side effects of treatment, medical history, concomitant medication, course of the underlying disease and trial procedures.

Possibly related: an AE which can medically (pharmacologically/clinically) be attributed to the study treatment.

Unrelated: an AE which is not reasonably related to the study treatment. A reasonable alternative explanation must be available.

An AE that is determined to be related to the administration of a study product is referred to as an "adverse drug reaction."

Page 71 of 176

6.1.3 Expectedness

Expected adverse drug reaction: Any AE possibly related to the co-administration of ivermectin-albendazole reported in the literature or on the drug package leaflets and listed in the consent form.

Unexpected adverse drug reaction: Any AE possibly related to the study product administration, the nature, frequency, specificity or severity of which is unanticipated and not consistent with the available risk information described for these drugs.

6.1.4 Serious adverse events

According to the ICH "Clinical Safety Data Management: Definitions and standards for expedited Reporting E2A" [32], a serious adverse event (SAE) includes any event (experience) or reaction in any untoward medical occurrence that at any dose:

- 1. results in death;
- 2. is life threatening, meaning, the subject was, in the view of the Investigator, at immediate risk of death from the reaction as it occurred, *i.e.* it does not include a reaction that, had it occurred in a more serious form, might have caused death;
- 3. results in persistent or significant disability/incapacity, *i.e.* the event causes a substantial disruption of a person's ability to conduct normal life functions;
- 4. requires in patient hospitalization or prolongation of existing hospitalization;
- 5. creates a congenital anomaly or birth defect (not relevant for this study);
- 6. is an important medical event, based upon appropriate medical judgment, that may jeopardize the patient or subject or may require medical or surgical intervention to prevent one of the other outcomes defining serious.

A "severe" AE does not necessarily meet the criteria for a "serious" AE. Serious AEs are reported from consent to 24 hours post-treatment (Day 2).

SAEs that are still ongoing at the end of the study period will be followed up to determine the final outcome.

The causality of any SAE that occurs after the study period and its possible relatedness to the study treatment or study participation will also be assessed by investigators as described in section 6.1.2.

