4.6 Schedule of visits

Page 67 of 176

	Screenin g	Baseline/Treatment/Safety			Follow up				
	-21 to -1 days	Hours			Days				
		0		3	24	21	180	185	360
Diagnosis (stool examination)	Х					Х	Х		Х
Gut morbidity (stool RDTs)	Х					Х	Х		Х
Informed consent	Х		tment						
Demographics	Х		treat					ent	
Medical history		Х	1 and					eatme	
Clinical examination		Х	zatio				Х	re-tro	Х
Pregnancy testing		Х	domi				Х	ctive	
Hemoglobin measurement		Х	Ran				Х	Sele	Х
W. bancrofti co-infection		Х					Х		Х
Physical functioning		Х					Х		Х
Capturing AEs				Х	Х	Х			
Capturing SAE				Х	Х	Х			
Treatment satisfaction				Х		Х	Х		

 Table 1. Schedule of visits of longitudinal study.

5. Selection of the trial subjects

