6.2 Methods of recording and assessing adverse events

Subjects will be kept for observation for at least 3 hours following treatment for any acute AEs. If there is any abnormal finding, the local study physician will perform a full clinical and physical examination and findings will be recorded. An emergency kit will be available on site to treat any medical conditions that warrant urgent medical intervention. In addition patients will also be interviewed 3 and 24 hours and again 3 weeks after treatment about the occurrence of AEs (see chapter 4.6).

Information on all AEs (onset, duration, intensity, seriousness and causality) will be immediately entered in the appropriate AE module of the case report form (CRF) that serves as source document. For all AEs, sufficient information will be pursued and/or obtained so as to permit i) an adequate determination of the seriousness of the

Page 72 of 176

event (i.e. whether the event should be classified as a SAE); ii) an assessment of the casual relationship between the AE and the study treatments and iii) an assessment of intensity of AEs will be judged by the study physician.

All SAEs or SUSARs must be reported as described in Section 6.3.

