6.3 Reporting of serious adverse events

Any study-related unanticipated problem posing risk of harm to subjects or others (including all unexpected adverse drug reactions), and any type of SAE will be immediately (within a maximum of 24 hours after becoming aware of the event) notified to the study sponsor-investigator and co-PIs:

[name]. [name] (Sponsor-investigator)

Swiss Tropical and Public Health Institute [name] [contact] [contact]

E-mail: [contact]

[name] (Co-PI)

Public Health Laboratory Ivo de Carneri

[name]

Pemba, Zanzibar (Tanzania)

[contact]

[contact]

[contact]

Email: [contact]

Within the following 48 hours, the local co-investigator must provide to study sponsor-investigator further information on the SAE or the unanticipated problem in the form of a written narrative. This should include a copy of a completed SAE form, and any other diagnostic information that will assist the understanding of the event. In exceptional circumstances, a SAE may be reported by telephone. In these cases, a written report must
be sent immediately thereafter by fax or e-mail. Names, addresses and telephone for SAE reporting will be included in the trial-specific SAE form. Relevant pages from the CRF may be provided in parallel (e.g., medical history, concomitant medications).

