6.1.4 Serious adverse events

According to the ICH "Clinical Safety Data Management: Definitions and standards for expedited Reporting E2A" [33], a serious adverse event (SAE) includes any event (experience) or reaction in any untoward medical occurrence that at any dose:

- 1. results in death;
- 2. is life threatening, meaning, the subject was, in the view of the Investigator, at immediate risk of death from the reaction as it occurred, *i.e.* it does not include a reaction that, had it occurred in a more serious form, might have caused death;
- 3. results in persistent or significant disability/incapacity, *i.e.* the event causes a substantial disruption of a person's ability to conduct normal life functions;
- 4. requires in patient hospitalization or prolongation of existing hospitalization;
- 5. creates a congenital anomaly or birth defect (not relevant for this study);
- 6. is an important medical event, based upon appropriate medical judgment, that may jeopardize the patient or subject or may require medical or surgical intervention to prevent one of the other outcomes defining serious.

A "severe" AE does not necessarily meet the criteria for a "serious" AE. SAEs are reported from consent to 3 weeks post-treatment (Day 21).

SAEs that are still ongoing at the end of the study period will be followed up to determine the final outcome.

Page 153 of 176

The causality of any SAE that occurs after the study period and its possible relatedness to the study treatment or study participation will also be assessed by investigators as described in section 6.1.2.

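### The Pemba protocol contradicts itself on the SAE reporting period: Section 6.1.4 ends it at 24 hours, while its other safety sections run to day 21 or set no limit

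*Combined protocol and SAP*

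**What the plan says.** Pemba protocol, Section 6.1.4, sets the SAE window: "Serious AEs are reported from consent to 24 hours post-treatment (Day 2". No other sentence in that protocol defines a period for SAE reporting.

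Four other places in the Pemba protocol bear on the same question:

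- Section 6.1, on all adverse events: "The observation time for AEs starts when the treatment is initiated until day 21 (3 weeks after last drug administration".
- Section 4.6, visit schedule: the row "Capturing SAE" is marked at 3 hours, 24 hours and day 21.
- Section 6.2: "In addition patients will also be interviewed 3 and 24 hours and again 3 weeks after treatment about the occurrence of AEs". It then adds: "All SAEs or SUSARs must be reported as described in Section 6.3".
- Section 6.3: "any type of SAE will be immediately (within a maximum of 24 hours after becoming aware of the event) notified to the study sponsor-investigator". The trigger is awareness of the event, and no cut-off by time since treatment is given.

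In the Swiss, Côte d'Ivoire and Laos protocols, the sentence in the same position of Section 6.1.4 reads: "SAEs are reported from consent to 3 weeks post-treatment (Day 21". The time and events table in the SAP also marks SAE capture at day 21.

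**The concern.** On its face, Section 6.1.4 gives the gravest events a shorter reporting window than ordinary ones. A mild headache on day 10 falls inside Pemba's AE window, while a hospitalisation on day 10 falls outside the SAE window of 6.1.4. Site staff who look up the reporting period will find it only there.

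Pemba Section 10.4 establishes no data and safety monitoring board, so SAE notifications to the sponsor and the ethics committees are the main route by which a safety problem would surface during the trial. Pemba Section 4.3.1 also notes more adverse events with this combination in patients with filarial disease, and tests participants for *W. bancrofti*. If sites applied different windows, an SAE count from Pemba would cover a shorter period after dosing than a count from Laos or Côte d'Ivoire, and the two could not be set side by side.

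**Working it through.** The plan gives no figure to reproduce. The check is a comparison of texts, followed by the length of the disputed interval.

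**Step 1. Is the 24-hour sentence current?** The SAP introduction names Pemba v1.01 of 13.2.18 as the version it rests on. The Pemba synopsis prints the same version number and date. The sentence is therefore live and not superseded.

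**Step 2. Is it a declared country difference?** For Pemba, the supplement overview lists the absence of the dose-finding study, venous blood sampling, malaria testing and *S. stercoralis* diagnosis, and the addition of microbiome samples. It lists no shorter SAE window. The history of protocol changes has no entry on it either.

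**Step 3. What does each Pemba section imply for an SAE on day 10?**

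| Pemba section | Period or trigger | SAE on day 10 |
|---|---|---|
| 6.1.4, window sentence | consent to 24 hours after treatment | outside |
| 6.1 | start of treatment to day 21 | inside, as an AE |
| 4.6 | SAE capture at 3 h, 24 h, day 21 | captured at day 21 |
| 6.2 | interview at 3 weeks; all SAEs go to 6.3 | inside |
| 6.3 | any SAE, within 24 h of awareness | inside |
| 6.4 | ethics timelines; the one for non-fatal, non-life-threatening SAEs runs from the sponsor's first knowledge | no cut-off by time since treatment |

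One sentence stands against five sections. The 24 hours in 6.3 is a delay from awareness to notification, so it cannot be the source or the meaning of the 24 hours in 6.1.4.

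**Step 4. How long is the disputed interval?** Inputs: AE observation of 21 days after treatment (6.1), and an SAE window ending at 24 hours, labelled Day 2 (6.1.4). Section 5.5 places treatment on day 0, so 24 hours later is day 1 and the label does not match the duration. Both readings are shown:

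- Cut-off at 24 hours: 21 − 1 = 20 days outside; 20/21 = 95%.
- Cut-off at day 2: 21 − 2 = 19 days outside; 19/21 = 90%.

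These are shares of post-treatment days only. The SAE window opens at consent, before treatment. The interval concerns the 600 participants planned at Pemba, 300 per arm (Section 7.2).

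**Step 5. Does a planned analysis depend on it?** The SAP safety section describes adverse events by country in two tables. Neither has an SAE row, the total columns and rows add the arms and not the countries, and the first table has a column for events after 24 hours. No pooled SAE analysis is specified.

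**The case against.** The strongest reply is that the protocol already covers the gap. Section 6.2 sends all SAEs to 6.3, Section 6.3 requires any type of SAE to be notified on awareness, and Section 6.4 sets no limit by time since treatment. Seriousness is recorded on the CRF for every adverse event, including those learned at the 3-week interview. Even 6.1.4 provides for late events, in the sentence that begins "The causality of any SAE that occurs after the study period". On this view, a day-10 hospitalisation is reportable at Pemba, and 6.1.4 contains a drafting slip.

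Much of this stands. A reader might infer from 6.1.4 that Pemba sites have no duty to report SAEs after 24 hours, or that SAEs from day 2 to day 21 will be missing and the Pemba count biased low. The documents do not support either inference, because Sections 6.2 and 6.3 say the opposite and the day-21 visit captures SAEs. Nor do they support a contrast in the upper confidence limit for an SAE rate between a one-day window at Pemba and three weeks elsewhere. That would assume no capture after 24 hours, which the visit schedule contradicts.

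The reply does not remove the contradiction. Section 6.3 says how and how fast to report, whereas 6.1.4 alone says for what period. A site can reasonably read the specific window as limiting the general procedure. The sentence on events after the study period asks for a causality assessment, which is not the same as notification.

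**Conclusion.** The Pemba protocol contradicts itself on the SAE reporting period, and the contradiction is in current text. It is best treated as an internal inconsistency and not as a deliberate design choice, since no document declares or justifies a shorter window for Pemba. Whether it is a drafting leftover cannot be established from the documents.

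The possible consequence is conditional. If a site followed 6.1.4 in preference to Sections 4.6, 6.2 and 6.3, SAEs from 19 or 20 of the 21 post-treatment days could go unreported, and Pemba SAE counts could be low and not comparable with the other countries. If sites followed the other sections, nothing would be lost. The primary endpoint is not affected, and no planned pooled SAE analysis is spoiled.

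The comparison with the other countries rests on the protocol texts as printed in the supplement. The dates printed in the Côte d'Ivoire and Laos synopses (12.06.2018 and 13.06.2018) are earlier than those of the versions the SAP cites (22.11.2018 and 19.09.2018). The contradiction within the Pemba protocol does not depend on that comparison.

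**What to change.** Reconcile Pemba Section 6.1.4 with Sections 4.6, 6.1, 6.2 and 6.3, so that the SAE reporting window is not shorter than the protocol's own AE window and day-21 SAE capture visit. Remove the mismatch between 24 hours and Day 2 in the same sentence. If a shorter window at Pemba was intended, the protocol should say so, justify it and list it among the country variations; the schedule and Sections 6.2 and 6.3 would then also need to be brought into line.

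The change is one sentence and needs no new visit, because the 3-week interview already takes place. It still needs the sponsor's signature and ethics committee approval under Pemba Section 8.1.

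If data are already collected, check the Pemba 3-week interviews and the CRF seriousness fields for SAEs after 24 hours. Do this before SAEs are reported or compared across countries, and state the period that each country's SAE count covers.

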6.1.5 Suspected unexpected serious adverse reactions

A suspected unexpected serious adverse reaction (SUSAR) is an unexpected adverse drug reaction which also meets the definition of SAEs.

6.2 Methods of recording and assessing adverse events

Subjects will be kept for observation for at least 3 hours following treatment for any acute AEs. If there is any abnormal finding, the local study physician will perform a full clinical and physical examination and findings will be recorded. An emergency kit will be available on site to treat any medical conditions that warrant urgent medical intervention. In addition patients will also be interviewed 3 and 24 hours and again 3 weeks after treatment about the occurrence of AEs (see chapter 4.6).

Information on all AEs (onset, duration, intensity, seriousness and causality) will be immediately entered in the appropriate AE module of the case report form (CRF) that serves as source document. For all AEs, sufficient information will be pursued and/or obtained so as to permit i) an adequate determination of the seriousness of the

Page 72 of 176

event (i.e. whether the event should be classified as a SAE); ii) an assessment of the casual relationship between the AE and the study treatments and iii) an assessment of intensity of AEs will be judged by the study physician.

All SAEs or SUSARs must be reported as described in Section 6.3.

6.3 Reporting of serious adverse events

Any study-related unanticipated problem posing risk of harm to subjects or others (including all unexpected adverse drug reactions), and any type of SAE will be immediately (within a maximum of 24 hours after becoming aware of the event) notified to the study sponsor-investigator and co-PIs:

[name]. [name] (Sponsor-investigator)

Swiss Tropical and Public Health Institute [name] [contact] [contact]

E-mail: [contact]

[name] (Co-PI)

Public Health Laboratory Ivo de Carneri

[name]

Pemba, Zanzibar (Tanzania)

[contact]

[contact]

[contact]

Email: [contact]

Within the following 48 hours, the local co-investigator must provide to study sponsor-investigator further information on the SAE or the unanticipated problem in the form of a written narrative. This should include a copy of a completed SAE form, and any other diagnostic information that will assist the understanding of the event. In exceptional circumstances, a SAE may be reported by telephone. In these cases, a written report must
be sent immediately thereafter by fax or e-mail. Names, addresses and telephone for SAE reporting will be included in the trial-specific SAE form. Relevant pages from the CRF may be provided in parallel (e.g., medical history, concomitant medications).

6.4 Safety reporting to Health Authorities and Ethics Committees

The sponsor-investigator will send appropriate safety notifications to Health Authorities in accordance with applicable laws and regulations. Additionally, this information will be provided to 'Ethikkomission Nordwestund Zentralschweiz' (EKNZ, Switzerland), and the 'Zanzibar Medical Research and Ethical Committee' (ZAMREC, Tanzania) in Zanzibar according to national rules. Fatal or life-threatening SAEs or SUSARs will be reported within 24 hours followed by a complete report within 7 additional calendar days. Other SAEs and SUSARs that are not fatal or life-threatening will be filed as soon as possible but no later than 14 days after first knowledge by the sponsor.

7. Statistics

7.1 Definition of primary endpoint

Cure rate of co-administered ivermectin-albendazole against *T. trichiura* is the primary endpoint in our study. Since this might be influenced by infection intensity, treatment groups will be equally balanced in terms of infection intensity by 2 levels of baseline infection intensity (light infections and moderate/heavy infections).

7.2 Justification of number of trial subjects

Based on available summarized efficacy measures from a recent review [1] and the published literature, we assume that the CR of albendazole against *T. trichiura* is 30% compared to 50% in the albendazole-ivermectin treatment regimen. To detect a difference with 90% power at a two-sided 5% significance level, we require 121 participants per study arm and 143 to account for potential loss to follow-up of 15%. We further assume the same treatment efficacy in the mid-term treatment and a 6-months reinfection risk of 10%. Consequently we expect a proportion of negative patients after 12 months of 44% in the albendazole arm and of 65% in the albendazole-ivermectin arm resulting in a required sample size of 111 participants per arm. To account for a loss to follow-up of 30% after 6 months and 40% at final assessment (12 months) we aim to recruit 300 participants in each group (600 in total). This number is largely sufficient to further show differences in efficacy in subgroups such as school-aged versus adult study populations without losing statistical power as long as individuals get recruited in similar proportions to these two groups.

7.3 Description of statistical methods

The primary available case analysis will include all participants with primary end point data. In addition, an intention-to-treat analysis will be conducted considering all participants with missing endpoint data as treatment failure or all as treatment success to ensure that the results are not sensitive to potential loss to follow-up bias. CRs will be calculated as the percentage of egg-positive children at baseline who become egg-negative after treatment. EPG will be assessed by adding up the egg counts from the quadruplicate Kato-Katz thick smears and multiplying this number by a factor of six. The ERR will be calculated as:

$$ERR = 1 - \frac{\frac{1}{n}e^{\sum \log(EPG_{follow} - up + 1)}}{\frac{1}{n}e^{\sum \log(EPG_{baseline} + 1)} - 1}$$

Page 74 of 176

In the primary model we estimate the difference among CRs by using unadjusted logistic regressions. In a subsequent analysis an adjusted logistic regression (adjustment for age, sex, community, weight and height) will be performed.

Geometric mean egg counts will be calculated for the different treatment arms before and after treatment to assess the corresponding ERRs. Bootstrap resampling method with 5,000 replicates will be used to calculate 95% confidence intervals (CIs) for ERRs and the difference between the ERRs.

Results from the stool RDT for fecal occult blood will be categorized as negative, trace and positive. For calprotectin, individuals with levels exceeding 50 μ g/g will be considered as positive and concentrations be classified into low (51–149 μ g/g), medium (150–299 μ g/g) and high (\geq 300 μ g/g) intensity [19].

Anthropometric measurements such as height, weight will be translated into weight- and height-related z-scores using readily available Stata macros calculating growth indicators for children 5-19 years [33]. Body mass index and indicators for muscle and fat tissue such as MUAC and triceps skinfold thickness will serve as indicators for all ages and further be classified using a percentiles approach to compare within populations [34].

Questionnaires on physical functioning and treatment satisfaction will be evaluated by creating summary scores by summing up and transforming the single question scores according to the following formula: [(actual raw score-lowest possible raw score)/(possible raw score range)]*100 [23].

Morbidity indicators with continuous values (e.g. anthropometric, Hb, mean physical functioning scores) will be compared in a first step within and between groups using independent and paired t-test statistics while chi-square testing will be performed for binary/categorical outcomes (e.g. anemia, malnutrition categories, fecal calprotectin intensity, blood in stool). To compare individual's changes in malnutrition categories as an effect from treatment McNemar's test will be applied. In a second step, adjusted repeated measures linear and logistic regressions using generalized estimating equation (GEE) models will be performed to assess development of morbidity indicators and related factors be investigated.

AEs will be evaluated descriptively as the difference of proportion reporting AEs before and after treatment.

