4.1 Primary and secondary endpoint

CR (primary end point, *i.e.* conversion from being egg positive pre-treatment to egg negative post-treatment) and ERR (secondary end point). In addition, diagnostic performance using different tools will be evaluated, *Trichuris* strains described using molecular characterization and safety and potential benefits on morbidity indicators from treatment assessed (secondary end points).

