4.3.2 Assessment of efficacy after treatment

The efficacy of the treatment will be determined 21 days post-treatment by collecting another two stool samples which will be microscopically examined for *T. trichiura* using duplicate Kato-Katz thick smears and potential co-infection with *S. stercoralis* applying the Baermann technique. Participants will be considered *T. trichiura* cured if no eggs have been found in the stool. EPG will be assessed by adding up the egg counts from the quadruplicate Kato-Katz thick smears and multiplying this number by a factor of six. Geometric and arithmetic mean egg counts will be calculated for the different treatment arms before and after treatment to assess the

corresponding ERRs. The stool samples collected 21 days post-treatment for efficacy assessment will further be re-tested with the same rapid diagnostic test and immunoassay used at baseline to determine fecal occult blood and calprotectin levels. Frequencies of subjects found positive with either of the two markers and by intensity category for calprotectin will be calculated by treatment arm.

At the end of the study (approximately 12 months post-treatment) all participants remaining positive for *T*. *trichiura* and other soil-transmitted helminths will be treated with albendazole-ivermectin, the currently best recommended treatment against *T*. *trichiura*.

Potential extended effects on follow-up helminth prevalences will be assessed using the same methodological approach as used for the efficacy assessment and will be based on stool samples collected 6 and 12 months post-treatment. Likewise fecal occult blood and calprotectin will be re-determined on the same stool samples.

To assess eventual reduction in morbidity indicators all trial participants will be asked to provide another fingerprick blood sample at the 6 and 12 month follow-up for Hb measurement. Anthropometric measurement including height, weight, MUAC and triceps skinfold thickness will be repeated on the same occasion. Children (6-16 years) will be asked to re-assess their own physical functioning in repeated questionnaire interviews during these two last follow-ups. Long-term satisfaction with the treatment will be asked 6 months past-treatment. Mean values for continuous outcomes and frequencies for binary/categorical outcomes will be calculated for each treatment arm and follow-up time point and compared using descriptive and repeated measurement analysis as detailed in section 7.3.

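### Pemba protocol, section 7.3: calprotectin is named only by its ordered bands in a chi-square comparison, which costs substantial power for a consistent shift if concentrations are recorded

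*Combined protocol and SAP*

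**What the plan says.** Pemba 7.3 first derives the gut markers. For calprotectin, "individuals with levels exceeding 50 μ g/g will be considered as positive and concentrations be classified into low", medium and high, with cuts at 50, 150 and 300 µg/g. With the negatives, that makes four ordered levels. For occult blood: "Results from the stool RDT for fecal occult blood will be categorized as negative, trace and positive".

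It then sets out a first-step comparison of morbidity indicators. Some go to t-tests: "Morbidity indicators with continuous values (e.g. anthropometric, Hb, mean physical functioning scores", where the list is given as examples. For the rest, "chi-square testing will be performed for binary/categorical outcomes (e.g. anemia, malnutrition categories, fecal calprotectin intensity, blood in stool". No trend, rank or ordinal method appears. A second step follows: "In a second step, adjusted repeated measures linear and logistic regressions using generalized estimating equation (GEE) models will be performed". It does not say whether calprotectin enters as a concentration, a positive/negative result or a band.

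Pemba 4.3.2 also plans a table: "Frequencies of subjects found positive with either of the two markers and by intensity category for calprotectin will be calculated by treatment arm". Pemba 4.1 gives the status of these outcomes: "safety and potential benefits on morbidity indicators from treatment assessed (secondary end points". The Pemba synopsis agrees and lists no exploratory endpoints; its objective (h) names occult blood and calprotectin among the morbidity indicators. The SAP is limited to the data collected three weeks after treatment and contains no gut-marker analysis, so Pemba 7.3 is the governing text here.

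**The concern.** Haemoglobin and anthropometry appear twice in that paragraph: once as continuous measurements and once through a category (anaemia, malnutrition). Calprotectin appears only through its category. Two losses follow if the chi-square test is an ordinary Pearson test on the bands. Banding discards the variation within each band. Ignoring the order then spends 3 degrees of freedom on what is essentially a one-direction question. A real difference between arms in gut inflammation could then be missed and reported as no benefit on a declared secondary endpoint.

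Occult blood has the same ordering problem at three levels (2 degrees of freedom), but it has no underlying concentration to lose.

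**Working it through.** **Inputs from Pemba 7.2.** The plan's figure for cure rates of 30% v 50%, 90% power and two-sided 5% reproduces with unpooled variance:
(1.960 + 1.282)² × (0.3×0.7 + 0.5×0.5) / 0.20² = 10.51 × 0.46 / 0.04 = 120.8, so 121 per arm; 121 / 0.85 = 142.4, so 143.
With 300 recruited per arm, 15% loss leaves 255 and 40% loss leaves 180. No power or sample size is stated for gut morbidity.

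**Assumed, because the documents give nothing.** Calprotectin is log-normal with median 30-100 µg/g and log SD 0.8-1.2. One arm is shifted downwards by a constant ratio, sized so that a t-test on log concentration has 80% power.

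**Step 1: cost of degrees of freedom alone.** 80% power on 1 df needs noncentrality λ = (1.960 + 0.842)² = 7.85. The 5% critical values are 3.84 (1 df), 5.99 (2 df) and 7.81 (3 df). At the same λ, power is 80%, 71% and 64.5%. This needs no distributional assumption.

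**Step 2: one worked case** (255 per arm, median 60, log SD 1.0).
- Shift on the log scale: 1.0 × 2.802 × √(2/255) = 0.248, a ratio of geometric means of 0.78.
- Band probabilities come from Φ((ln c − ln median)/SD) at c = 50, 150 and 300. Negative/low/medium/high is 0.428/0.393/0.126/0.054 in one arm and 0.526/0.352/0.091/0.032 in the other.
- Pearson: λ = n Σ (p − q)²/(p + q) = 6.1 on 3 df, power 53%.
- Rank test on the same bands: λ = 6.0 on 1 df, power 69%.

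Banding takes 80% to 69%, and ignoring the order takes 69% to 53%. Simulation of the same case (3,000 runs) gave 0.80 for log concentration, 0.70 for the rank test and 0.53 for Pearson.

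**Step 3: the range** over the assumed medians and SDs, at 255 and 180 per arm:

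| Comparison | Power |
|---|---|
| t-test, log concentration | 80% (by construction) |
| Rank test, four bands | 52-73% |
| Positive/negative chi-square | 51-61% |
| Pearson, four bands, 3 df | 37-57% |

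The worst case is median 30, SD 0.8, 180 per arm (37% and 52% for Pearson and rank). The best is median 100, SD 1.0, 255 per arm (57% and 73%). Loss of order accounts for about 15-16 points throughout. Banding accounts for the rest, 80 − 73 = 7 to 80 − 52 = 28 points.

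**Step 4: occult blood** (assumed splits negative/trace/positive).
- Proportional odds, with 85/10/5, 70/20/10 or 50/25/25%: where a rank test has 80% or 90% power, Pearson on 2 df has 71% or 83.5%, a loss of 6.5-9 points. An any-versus-none comparison has 77-80% or 88-90%, a loss of about 0-3 points.
- Simulation with a latent normal shift, 255 per arm: the ordered test gained about 6-15 points, for example 0.61 v 0.71 (70/20/10) and 0.55 v 0.69 (50/25/25).

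**Step 5: a case that goes the other way.** In a constructed setting where only the top band changed, Pearson had 70% power and the rank test 11%.

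**The case against.** The strongest reply is that the text is less committed than it looks. Four parts of it have force.

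1. **The continuous scale is not ruled out.** The continuous list is only of examples, haemoglobin and anthropometry are analysed both ways, and the chi-square test is only the unadjusted first step. A reader might infer that the GEE excludes concentration. The documents do not support that; the scale is unspecified. What remains is a gap to close.

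2. **Pearson is not named.** It is the natural reading of chi-square testing, but not the only one. For occult blood, the binary/categorical wording and the planned frequencies of positives in 4.3.2 leave a positive/negative comparison open, with almost no loss. Saying that both gut markers lose much of their power would go too far.

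3. **The assay may return only bands.** Pemba 7.3 speaks of concentrations and 4.3.1 of an immunoassay, but the visit schedule in 4.6 labels these measurements as stool RDTs. A continuous readout is therefore not established. If there is none, only the gain from respecting order is available.

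4. **The other countries are different.** A reader might extend the point to Laos, Côte d'Ivoire and the Swiss-approved protocol because they use the same bands. Their 7.3 sections name no chi-square test, allow logistic and linear regression as appropriate for morbidity indicators, and those protocols class the indicators as exploratory. Tabulating bands by arm is description, not a faulty test.

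It is also true that nothing is powered on gut morbidity and that all the calprotectin figures rest on assumed distributions. The qualitative result held in every consistent-shift setting tried; Step 5 shows that it does not hold for every pattern of effect.

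**Conclusion.** The point holds for calprotectin in the Pemba protocol, as an inexpensive improvement to a secondary analysis. Under a consistent shift and log-normal levels, an effect that log concentration would detect with 80% power is detected with about 37-57% by a four-band Pearson test and about 52-73% by a rank test on the bands. The full gain requires that concentrations are recorded; otherwise about 15-16 points are recoverable. For occult blood the gain is modest if three levels are tested and close to nil if the result is dichotomised. The primary cure-rate comparison is unaffected.

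**What to change.** In Pemba 7.3 only:

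- Where calprotectin concentrations are recorded, compare the arms at each follow-up on log concentration, adjusted for baseline log concentration, and state that the linear GEE uses this scale.
- Where the assay returns only bands, compare the arms with a Wilcoxon, trend or proportional-odds analysis.
- Use the same kind of ordered comparison for occult blood if it is kept at three levels.
- Keep the band frequencies by arm as description, so that an effect confined to one band stays visible.

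The cost is a wording change and one model per marker, with no new data, visits or participants. There are two downsides. The effect becomes a ratio of geometric means or a common odds ratio instead of a difference in percentages. And an ordered test can have less power than Pearson if the effect sits in a single band.
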